6.2 Toxicity Management

The toxicity management of the AEs including AESI consists of safety monitoring (review of AEs on an ongoing basis, and periodic/ad hoc unblinded review of safety issues by an internal safety DMC), interruption of study drug dosing with appropriate clinical management if applicable, and discontinuation of the subjects from study drug.

The management of specific AEs and laboratory parameters is discussed below and described in [Table 4](#). This includes AEs of serious infections, opportunistic infections, GI perforations, cardiovascular events (MACE), thromboembolic events, malignancies, and ECG abnormalities. This also includes the following laboratory abnormalities: hemoglobin, ANC, platelet count, ALT or AST, serum creatinine, CPK, lymphocyte count, total white blood cell (WBC) count, and urine protein to creatinine ratio (UPCR).

For all other AEs or laboratory-related AEs, study drug will be interrupted immediately if a subject experiences a confirmed severe (Grade 3) clinical AE or SAE for which the investigator considers the relationship to the study drug to be a reasonable possibility. For confirmed Grade 4 AEs for which the investigator considers the relationship to the study drug to be a reasonable possibility and the event does not improve back to at least Grade 2, then the study drug must be discontinued.

Product complaints concerning the investigational product must be reported to AbbVie within 1 business day of the study site's knowledge of the event. Product complaints occurring during the study will be followed up to a satisfactory conclusion.

All follow-up information is to be reported to the Sponsor (or an authorized representative) and documented in source as required by the Sponsor. Product complaints associated with AEs will be reported in the study summary. All other complaints will be monitored on an ongoing basis.

Management of Serious Infections

Subjects should be closely monitored for the development of signs and symptoms of infection during and after treatment with study drug. Study drug should be interrupted if a subject develops a serious infection (including COVID-19) or a serious opportunistic infection (excludes non-serious oropharyngeal candidiasis). A subject who develops a new infection during treatment with study drug should undergo prompt diagnostic testing appropriate for an immunocompromised subject. As appropriate, antimicrobial therapy should be initiated, and the subject should be closely monitored. Study drug may be restarted once the infection has been successfully treated. Subjects who develop active or latent TB must be discontinued from the study drug.

Canada only: Investigators should be advised to follow local public health guidelines in order to prevent subjects enrolled in these trials from acquiring TB.

COVID-19: Interrupt study drug in subjects with a confirmed diagnosis of COVID-19. Consider interrupting study drug in subjects with signs and/or symptoms and suspicion of COVID-19. The appropriate COVID-19 eCRFs should be completed. If a subject has a confirmed or suspected COVID-19 infection and study drug was interrupted, the investigator must contact the AbbVie TA MD before reintroducing study drug.

Management of Herpes Zoster

If a subject develops herpes zoster, the Investigator should consider temporarily interrupting study drug until the episode resolves.

Management of Serious Gastrointestinal Events

Subjects presenting with the onset of signs or symptoms of a serious GI event should be evaluated promptly for early diagnosis and treatment. If the diagnosis of GI perforation is confirmed, the subject must be discontinued from the study drug.

Management of Cardiovascular Events

Subjects presenting with potential cardiovascular events should be appropriately assessed and carefully monitored. These events will be reviewed and adjudicated by an independent CAC in a blinded manner.

Management of Malignancy

Subjects who develop malignancy other than NMSC or CIS of the cervix must be discontinued from the study drug. Information including histopathological results should be queried for the confirmation of the diagnosis. Periodic skin examination is recommended for subjects who are at increased risk for skin cancer.

Management of ECG Abnormality

Subjects must be discontinued from study drug for an ECG change considered clinically significant and with reasonable possibility of relationship to study drug OR a confirmed absolute Fridericia's correction formula (QTcF) value > 500 msec or confirmed increase of ≥ 60 msec from Baseline.

Management of Muscle-Related Symptoms

If a subject experiences symptoms suggestive of myositis or rhabdomyolysis, CPK and aldolase measurements should be requested and will be provided after review by the TA MD with clinical management and/or study drug interruption as deemed appropriate by the treating physician. Please refer to [Table 4](#) below for further instructions.

Management of Thrombosis Events

Subjects who develop symptoms of thrombosis should be promptly evaluated and treated appropriately. If the diagnosis of deep vein thrombosis, pulmonary embolus, or non-cardiac, non-neurologic arterial thrombosis is confirmed, the subject must be discontinued from study drug.

Management of Select Laboratory Abnormalities

For any given laboratory abnormality, the investigator should assess the subject and apply the standard of care for medical evaluation and treatment following any local guidelines. Specific toxicity management guidelines for abnormal laboratory values are described in [Table 4](#) and may require a supplemental eCRF to be completed (see Section 6.1 Complaints and Adverse Events). All abnormal laboratory tests that are considered clinically significant by the investigator will be followed to a satisfactory resolution. If a repeat test is required per [Table 4](#), the repeat testing must occur as soon as possible.

Table 4. Specific Toxicity Management Guidelines for Abnormal Laboratory Values

Laboratory Parameters	Toxicity Management Guidelines
Hemoglobin	
 • If hemoglobin < 8 g/dL interrupt study drug dosing and confirm by repeat testing with a new sample. • If hemoglobin decreases ≥ 3.0 g/dL from baseline without an alternative etiology, interrupt study drug dosing and confirm by repeat testing with new sample. • If hemoglobin decreases ≥ 3.0 g/dL from baseline and an alternative etiology is known, the subject may remain on study drug at the investigator's discretion. 
If confirmed, continue to withhold study drug until hemoglobin value returns to normal reference range or its baseline value.

Absolute neutrophil count (ANC)	
If confirmed < 750 cells/μL by repeat testing with new sample, interrupt study drug dosing until ANC value returns to normal reference range or its baseline value. Subjects who meet this criterion should be evaluated for an alternative etiology and closely monitored for infections.
 
 • The alternative etiology should be documented appropriately in the eCRF. If restarting study drug, documentation should include reason rechallenge is expected to be safe.
Platelet count	
If confirmed < 30,000 platelets/μL by repeat testing with new sample, interrupt study drug dosing until platelet count returns to normal reference range or its baseline value.

Laboratory Parameters	Toxicity Management Guidelines

Aspartate transaminase (AST) or alanine transaminase (ALT)
	
 • Interrupt study drug immediately if confirmed ALT or AST > 3 × upper limit of normal (ULN) by repeat testing with new sample and either a total bilirubin > 2 × ULN or an international normalized ratio (INR) > 1.5. 
 • INR will only need to be measured in subjects with ALT or AST > 3 × ULN by the central lab. A repeat test of INR is not needed for determination if above toxicity management criteria are met. • Interrupt study drug immediately if confirmed ALT or AST > 3 × ULN by repeat testing with new sample along with appearance of fatigue, nausea, vomiting, right upper quadrant pain or tenderness, fever, rash, and/or eosinophilia (> 5%). • Interrupt study drug immediately if ALT or AST > 5 × ULN by repeat testing with new sample. • Interrupt study drug immediately if ALT or AST > 8 × ULN and contact the AbbVie TA MD. 
Subjects who meet any of the above criteria should be evaluated for an alternative etiology of the ALT or AST elevation and managed as medically appropriate. The investigator should contact the AbbVie Therapeutic Area MD (TA MD) to discuss the management of a subject when an alternative etiology has been determined. The alternative etiology should be documented appropriately in the eCRF; study drug should be discontinued if no alternative etiology can be found.
 
For any confirmed ALT or AST elevations > 3 ULN, complete supplemental hepatic eCRF.
 
 • Subjects with HBc Ab+ (irrespective of HBs Ab status) and negative HBV DNA at Screening who develop the following should have HBV DNA by PCR testing performed within one week: 
 • ALT > 5 × ULN OR • ALT or AST > 3 × ULN if an alternative cause is not readily identified. 
A positive result for HBV DNA PCR testing in these subjects will require immediate interruption of study drug (per local guidelines) and a hepatologist consultation should occur within one week for recommendation regarding subsequent treatment.


Serum Creatinine
	
 • If serum creatinine is > 1.5 × the baseline value and > ULN, repeat the test for serum creatinine (with subject in an euvoletic state) to confirm the results. If the results of the repeat testing still meet this criterion then interrupt study drug and re-start study drug once serum creatinine returns to ≤ 1.5 × baseline value and ≤ ULN. • If confirmed new serum creatinine ≥ 2 mg/dL interrupt study drug, and re-start study drug once serum creatinine returns to normal reference range or its baseline value. 
For the above serum creatinine elevation scenarios, complete supplemental renal eCRF(s).

Laboratory Parameters	Toxicity Management Guidelines
Creatine Phosphokinase (CPK)	
 CPK and aldolase will be measured at every visit but results will be blinded to sites and subjects, as CPK elevation is a known class effect of JAK inhibitors and the results could be unblinding to the sites. If symptomatic myositis is suspected, the site may send a request to the AbbVie TA MD for CPK and/or aldolase results to be unblinded. Request must be approved by the AbbVie TA MD. If confirmed CPK $\geq 4 \times$ ULN accompanied by symptoms suggestive of myositis or rhabdomyolysis, interrupt study drug, complete supplemental CPK eCRF, and contact AbbVie TA MD.
Lymphocyte Count Decreased	
 If confirmed Grade 4 ($< 200/\text{mm}^3$) by repeat testing with new sample, interrupt study drug dosing until lymphocyte count returns to at least Grade 2 (< 800 to $500/\text{mm}^3$) or its baseline value.
White Blood Cell Count Decreased	
 If confirmed Grade 4 ($< 1000/\text{mm}^3$) by repeat testing with new sample, interrupt study drug dosing until white blood cell count returns to at least Grade 2 (< 3000 to $2000/\text{mm}^3$) or its baseline value.
Urine Protein to Creatinine Ratio	
 If > 1 g/day equivalent (1 mg/mg), repeat by testing with new sample, and if confirmed, a renal biopsy will be required. If Class IV lupus nephritis is confirmed, subject must be permanently discontinued from study drug.

eCRF = electronic case report form; HBc Ab+ = hepatitis B core antibody positive; HBs Ab = hepatitis B surface antibody; HBV = hepatitis B virus; INR = international normalized ratio; JAK = Janus kinase; PCR = polymerase chain reaction; TA MD = Therapeutic Area Medical Director; ULN = upper limit of normal

For all other AEs or laboratory-related AEs, study drug will be interrupted immediately if a subject experiences a confirmed severe (Grade 3) clinical AE or SAE for which the investigator considers the relationship to the study drug to be a reasonable possibility. For confirmed Grade 4 AEs for which the investigator considers the relationship to the study drug to be a reasonable possibility and the event does not improve back to at least Grade 2, then the study drug must be discontinued.

7 STATISTICAL METHODS & DETERMINATION OF SAMPLE SIZE

7.1 Statistical and Analytical Plans

Complete and specific details of the statistical analysis will be described and fully documented in the Statistical Analysis Plan (SAP). An unblinded interim analysis will be performed by an independent team at AbbVie after 50% of the planned subjects have completed Week 24 assessments. The study team will remain blinded until the Week 24 Primary Analysis. The Week 24 Primary Analysis will be conducted after all ongoing subjects have completed Week 24 assessments or have discontinued the study to inform next phase studies. The Final Analysis will be conducted when all subjects have completed the study.

Efficacy and safety analysis may be revised accordingly based on the IERC decision at the interim analysis.

Details will be included in the SAP.

7.2 Definition for Analysis Populations

The Full Analysis Set (FAS) includes all randomized subjects who have received at least 1 dose of study drug. Subjects will be grouped according to treatment as randomized. The FAS will be used for all efficacy and baseline analysis.

The Safety Analysis Set consists of all subjects who have received at least 1 dose of study drug. For the Safety Analysis Set, subjects are assigned to a treatment group based on the treatment actually received, regardless of the treatment randomized.

7.3 Statistical Analyses for Efficacy

Primary Endpoint Analysis

The primary efficacy endpoint, the achievement of SRI-4 and steroid dose ≤ 10 mg prednisone equivalent QD at Week 24, will be assessed for each active treatment group vs the placebo group. The treatment difference will be evaluated using a Cochran-Mantel-Haenszel (CMH) test stratified by randomization stratification factors. ABBV-599 (elsubrutinib/upadacitinib) combination treatment groups will be compared to placebo and the monotherapy treatment groups. Additional comparisons or analyses will be conducted as appropriate. There will be no multiplicity adjustment for the multiple comparisons.

The Week 24 Primary Analysis will be performed when all subjects have completed the Week 24 assessments or have discontinued the study. The Final Analysis will be performed after all subjects have completed all study assessments including the 30-day follow-up phone call.

Non-Responder Imputation while incorporating Multiple Imputation to handle missing data due to **COVID-19 (NRI-C)** will be applied for primary endpoint analysis. As observed (AO) analysis will be performed as the sensitivity analysis for the primary endpoint.

Secondary and Additional Endpoint Analysis

All secondary and additional efficacy endpoints described in Section 3.3 and Section 3.4 will be analyzed as follows:

Categorical variables will be tabulated by the number and frequency. Between-treatment group comparison will be evaluated in the same way as the primary endpoint analysis.

All continuous endpoints will be evaluated through the change from Baseline. For continuous endpoints with multiple post-Baseline visits, the treatment effect will be assessed through Mixed-effect Model Repeated Measures (MMRM) with treatment, visit and treatment-by-visit interaction, main stratification factors, and the continuous fixed covariate of baseline measurement. An unstructured variance covariance matrix will be used. For continuous endpoints with single post-Baseline visit analysis, the

treatment effect may be assessed through analysis of covariance with baseline value, treatment, and stratification factors as covariates. In addition, the descriptive statistics for continuous variables will be provided including sample size, mean, standard deviation, median, minimum, and maximum.

For the count endpoints (e.g., number of flares), negative binomial regression model will be used to assess treatment effect with treatment, visit, and stratification factors as covariates.

The Cox Proportional Hazards model will be used to assess the treatment effect for the time-to-event endpoint, i.e., time to flare.

Missing Data Imputation Definition

Censoring: For the time-to-event endpoint, i.e., time to flare, missing data will be considered as censored at the last available time for the information.

NRI-C: The NRI-C will categorize any subject who does not have an evaluation during a pre-specified visit window as a non-responder for the visit, except for missing data due to COVID-19 infection or logistical restriction, which will be handled by Multiple Imputation. In addition, subjects who prematurely discontinue from study drug will be considered as non-responders for all subsequent visits after discontinuation. Subjects will also be classified as non-responders as described in Section 5.4.

As Observed: As observed analysis will not impute values for missing evaluations, and thus a subject who does not have an evaluation on a scheduled visit will be excluded from the AO analysis for that visit. Regardless of premature discontinuation of study drug, all observed data will be used in the analysis. As observed analysis may be used for both categorical variables and continuous variables for sensitivity analysis.

Mixed-Effect Model Repeated Measurements: MMRM analysis will be conducted using a mixed-effect model for continuous variables. Data collected after study drug discontinuation or initiation of rescue treatment will not be included. The mixed model includes the categorical fixed effects of treatment, visit and treatment-by-visit interaction, main stratification factors, and the continuous fixed covariate of baseline measurement. An unstructured variance covariance matrix will be used. The parameter estimations are based on the assumption of data being missing at random and using the method of restricted maximum likelihood (REML).

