3.3 Secondary Endpoints

The following secondary efficacy endpoints will be evaluated:

1. Achievement of SRI-4 at Week 24
2. Achievement of BILAG-Based Combined Lupus Assessment (BICLA) response at Week 24
3. Achievement of Lupus Low Disease Activity State (LLDAS) at Week 24
4. Steroid burden, assessed as change from Baseline at Week 24
5. Number of mild, moderate, or severe flares per patient-year (respectively and overall) by Safety of Estrogens in Lupus Erythematosus National Assessment (SELENA) SLEDAI Flare Index (SFI), assessed by number and types of flare per subject through Week 24

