5.4 Concomitant Therapy

Subjects taking the following concomitant medications/therapy are required to follow the directives below:

Allowed Concomitant Medications/Therapy	Comments/Notes
Methotrexate	≤ 20 mg/wk with concomitant folic acid ≥ 5 mg/wk
Azathioprine	≤ 150 mg/day
Mycophenolate mofetil	≤ 2,000 mg/day
Mycophenolate sodium	≤ 1,440 mg/day
Hydroxychloroquine	≤ 400 mg/day
Chloroquine	≤ 500 mg/day
Quinacrine	≤ 100 mg/day
Leflunomide	≤ 20 mg/day
Cyclosporine	Dosed by serum levels
Tacrolimus	Dosed by serum levels
Corticosteroids (prednisone-equivalent)	≤ 20 mg/day, decrease no faster than 5 mg QD per week

Rescue Concomitant Medications/Therapy	Comments/Notes
Corticosteroids (prednisone-equivalent)	Increase of no more than 5 mg QD per week regardless of Baseline dose, maximum dose of 25 mg, through Week 8

Subject must remain on their background therapy throughout the entirety of the study. The only permitted change of background therapy is steroid tapering. If applicable, subjects should continue on their stable doses of nonsteroidal anti-inflammatory drugs (NSAIDs), acetaminophen, and low-potency narcotics. For NSAIDs, acetaminophen/paracetamol, tramadol, codeine, hydrocodone, and propoxyphene that are part of background therapy, changes in dose, including initiation, are not allowed, with the exception of protocol-defined rescue therapy. The following medications taken as needed (PRN) are allowed but should not be taken within the 24 hours prior to any study visit: NSAIDs, acetaminophen/paracetamol, tramadol, codeine, hydrocodone, and propoxyphene. In the event of tolerability (or other safety) issues, the doses of NSAID and/or acetaminophen may be decreased or discontinued with substitution of another NSAID.

Note: If medication supply issues result in a change in background therapy due to pandemic changes, substitutions meeting protocol requirements are permitted and must be approved by the AbbVie Therapeutic Area Medical Director (TA MD).

Any medication or vaccine (including over the counter or prescription medicines, vitamins, and/or herbal supplements) that the subject is receiving at the time of enrollment or receives during the study must be recorded through the post-treatment visit (30-day follow-up phone call).

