MMRM analysis will be conducted using a mixed-effect model including observed measurements at all visits for continuous variables. Data collected on or after initiation of rescue treatment or after initiation or dose escalation of SLE-related corticosteroid as defined in [Section 8.2.2](#) will not be included. The mixed model includes the categorical fixed effects of treatment, visit and treatment-by-visit interaction, randomization stratification factors, and the continuous fixed covariate of baseline measurement. An unstructured variance covariance matrix will be used. The parameter estimations are based on the assumption of data being missing at random and using the method of restricted maximum likelihood (REML).

As Observed (AO)

AO analysis will not impute values for missing evaluations, and thus a subject who does not have an evaluation on a scheduled visit will be excluded from the AO analysis for that visit. Regardless of premature discontinuation of study drug or initiation of rescue treatment or initiation or dose escalation of SLE-related corticosteroid as defined in

Section 8.2.2, all observed data will be used in the analysis. As observed analysis may be used for both categorical variables and continuous variables for sensitivity analysis.

Multiple Imputation (MI)

As a sensitivity analysis, MI will be utilized for the primary endpoint. Data collected on or after the occurrence of intercurrent events defined in Section 8.2.2 will be considered as non-responder. When a subject is a responder at both before and after the visit window, the subject will be categorized as a responder for the visit. Otherwise, subjects who have no available measurements will be handled by multiple imputations. Details on MI can be found in NRI-C approach.

Observed Case (OC)

The OC analysis will not impute values for missing evaluations and, thus, a subject who does not have an evaluation on a scheduled visit will be excluded from OC analysis for that visit. In addition, the OC analysis will not use values on or after the occurrence of intercurrent events defined in Section 8.2.2.

Censoring

For the time-to-event endpoint, i.e., time to flare, missing data will be considered as censored at the last available time for the information.

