* Note: In the event the study is partially terminated, terminated groups will be removed from the comparison.

The binary secondary endpoints will be analyzed using the same approach as that for primary endpoint as specified in Section 8.4.2. Specifically, CMH adjusting for randomization stratification factors will be used to construct the treatment difference, the associated 95% CI and p-value between treatment group comparison. The NRI-C will be the primary approach for missing data handling in the analyses of binary secondary efficacy endpoints.

All continuous endpoints will be evaluated through the change from Baseline. For continuous endpoints with multiple post-Baseline visits, the treatment effect will be assessed through Mixed-effect Model Repeated Measures (MMRM) with treatment, visit

and treatment-by-visit interaction, randomization stratification factors, and the continuous fixed covariate of baseline measurement. An unstructured variance covariance matrix will be used. For continuous endpoints with a single post-baseline visit, the treatment effect may be assessed through analysis of covariance (ANCOVA) with baseline value, treatment, and randomization stratification factors as covariates. In addition, the descriptive statistics for continuous variables will be provided including sample size, mean, standard deviation, median, minimum and maximum.

For the count endpoint (e.g., number of flares by SLENAI SFI), negative binomial regression model will be used to assess treatment effect with treatment, and randomization stratification factors as covariates.

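### The MMRM holds one baseline slope across all visits, so the Week 24 contrast for steroid burden is likely under-adjusted for baseline dose and less precise than it could be

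*Protocol*

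**What the plan says.** The model is stated four times, always with the same structure.

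- Protocol 7.3, secondary and additional endpoints: "treatment, visit and treatment-by-visit interaction, main stratification factors, and the continuous fixed covariate of baseline measurement". It adds: "An unstructured variance covariance matrix will be used".
- Protocol 7.3, missing data definitions: "main stratification factors, and the continuous fixed covariate of baseline measurement".
- SAP 8.3, MMRM paragraph: "visit and treatment-by-visit interaction, randomization stratification factors, and the continuous fixed covariate of baseline measurement".
- SAP 8.5.2: "and treatment-by-visit interaction, randomization stratification factors, and the continuous fixed covariate of baseline measurement".

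Treatment is crossed with visit. Baseline and the stratification factors are not, and no reason is given for holding their effects constant.

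The only continuous secondary endpoint is "Steroid burden, assessed as change from Baseline at Week 24" (Protocol 3.3). On steroid dose, Protocol 5.1 (criterion 10) requires background therapy to be stable for 30 days before Baseline. Protocol 5.4 makes tapering the only allowed change to background therapy, caps background dose at 20 mg/day, and limits tapering: "decrease no faster than 5 mg QD per week". Appendix D schedules steroid assessment from Week 2, whereas SLEDAI-2K, BILAG and CLASI have their first post-baseline assessment at Week 4.

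**The concern.** A common slope is harmless if baseline predicts change equally well at every visit. Steroid dose is a natural exception. At the permitted maximum rate a subject on 20 mg can have come down by at most 2 × 5 = 10 mg at Week 2, but could be at zero by Week 24. A subject on 5 mg can never drop by more than 5 mg. If tapering is spread over the weeks, the slope of change on baseline dose starts near zero and steepens.

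Generalised least squares does not average the visit slopes evenly. It favours visits with small residual variance, here the early ones where few subjects have changed dose. The fitted slope is then close to the early slope, and part of the baseline-related scatter at Week 24 stays in the residual. The 10 mg stratum does not repair this, because its effect is also held constant over visits. At stake is precision on secondary endpoint 4 and, to a lesser degree, on the other continuous endpoints.

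**Working it through.** **The plan's own figure.** The only sizing statement is for the binary primary endpoint: 65 per group, 25% against 45% or 50%, two-sided alpha 0.10 (Protocol 7.7). With the pooled variance under the null,

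power = Φ{[δ − 1.645·√(2p̄q̄/n)] / √[(p₁q₁ + p₂q₂)/n]}.

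- 25% vs 45%: (0.20 − 1.645 × 0.0837)/0.0818 = 0.76, giving 77.7%.
- 25% vs 50%: (0.25 − 1.645 × 0.0849)/0.0820 = 1.34, giving 91.1%.

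The stated 78% to 91% reproduces and does not involve the MMRM. No such figure exists for a continuous endpoint.

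**Formula.** With complete data, let β be the vector of visit slopes of change on baseline and S the residual covariance given baseline.

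- Common slope: b = 1′S⁻¹β / 1′S⁻¹1.
- Variance of a pairwise Week 24 contrast: (2/n)·[S₂₄ + (β₂₄ − b)²·Var(baseline)].
- With visit-specific slopes the second term vanishes, so the SE ratio is √[1 + (β₂₄ − b)²·Var(baseline)/S₂₄].

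**Generic score (all inputs assumed).** Take unit variance at every visit, a baseline correlation of 0.9 at Week 2 and 0.5 at Week 24. Then β₂ = −0.10, β₂₄ = −0.50 and S₂₄ = 1 − 0.25 = 0.75.

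- Compound-symmetric correlation 0.3: b = −0.15; √(1 + 0.35²/0.75) ≈ 1.08.
- Compound-symmetric correlation 0.6: b = −0.03; √(1 + 0.47²/0.75) ≈ 1.14. Here b is nearer zero than even the Week 2 slope, because strong correlation can give late visits negative weight.
- No baseline adjustment at all: √(1 + 0.50²/0.75) = 1.155.

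| Assumed baseline correlation, first visit / Week 24 | SE ratio at Week 24 |
|---|---|
| 0.5 / 0.5, first visit Week 2 | 1.00 |
| 0.7 / 0.5, first visit Week 2 | 1.01–1.02 |
| 0.8 / 0.5, first visit Week 2 | 1.03–1.06 |
| 0.9 / 0.5, first visit Week 2 | 1.08–1.14 |
| 0.9 / 0.4, first visit Week 2 | 1.11–1.19 |
| 0.9 / 0.5, Week 4 start (SLEDAI-2K type) | 1.05–1.09 |

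In the 0.7/0.5 case 90% to 94% of the benefit of baseline adjustment is kept. In the 0.9/0.5 case with a Week 2 visit it is 11% to 52%.

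**Steroid burden.** Simulated trials of 5 × 65, with an assumed dose mix and capped taper (600 replicates per setting; slopes from one illustrative replicate):

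| Share tapering | Common slope | Week 24 slope | SE, planned model | SE, visit-specific | Ratio | Ratio, unadjusted |
|---|---|---|---|---|---|---|
| 30% | −0.006 | −0.23 | 0.573 | 0.550 | 1.04 | 1.04 |
| 50% | −0.010 | −0.25 | 0.675 | 0.621 | 1.09 | 1.09 |
| 80% | −0.025 | −0.44 | 0.713 | 0.581 | 1.23 | 1.25 |

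In these settings the planned model is close to unadjusted. Adding the 10 mg stratum as a main effect left the ratios unchanged (1.04, 1.09, 1.23).

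Other assumed patterns bracket this. With 30% to 70% tapering and a mean start at Week 8 or 16, the SE was 5% to 20% wider. In a large-sample calculation with partial tapers, mean start between Week 1 and 16 and rates of 1.25 or 5 mg/week, it was 1.6% to 14% wider; early starts at the maximum rate gave a variance excess of only 3% to 14%. In every pattern the common slope was nearer zero than the Week 24 slope. Overall the SE is about 2% to 23% wider, a variance excess of about 3% to 50%. On the reported SE, that is the precision of 65/1.02² ≈ 62 down to 65/1.23² ≈ 43 subjects per arm.

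**Interval coverage.** In the 50% row above, the model SE and the empirical SD agree (0.675 vs 0.683). With allocation stratified at 10 mg, as planned, the actual baseline imbalance is smaller than the model assumes. At 70% tapering with a mean start at Week 8, the model SE was 0.753 against an empirical SD of 0.658. Across stratified runs 90% intervals covered about 90% to 96%.

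**The case against.** The strongest reply is that every magnitude is assumed. The documents give no slope, SD or correlation for any continuous endpoint and do not say when or how often subjects taper. Protocol 5.4 sets a ceiling on the taper rate, not a schedule: at 5 mg per week a subject on 20 mg could reach zero by Week 4. If most tapering came that early, the slopes would differ less and the loss would be near the low end. This stands, and it is why the size is given as a range starting near 2%.

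Data handling is also simplified. SAP 8.3 drops observations on or after initiation or escalation of SLE-related corticosteroid, under rules blacked out in SAP 8.2.2. That acts directly on this endpoint, and dropout was not modelled. Any arm terminated after the interim analysis gets descriptive statistics only (SAP 8.1), so five arms of 65 may not apply. These limits bear on the size; they do not remove the mechanism.

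Three stronger readings might be inferred, and the documents do not support them:

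- That every continuous endpoint is barely adjusted at Week 24. With mild divergence of slopes over 90% of the benefit is kept, and SLEDAI-2K, BILAG and CLASI have no Week 2 visit to pull the slope.
- That the inference is invalid. With complete data randomisation keeps the contrast unbiased, and the intervals err, if at all, toward being conservative.
- That a chance baseline imbalance passes straight into the result. Stratification at 10 mg limits that imbalance.

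**Conclusion.** The point holds as a modest loss of efficiency, most credible for steroid burden. All four statements of the model force one baseline slope on all visits, and the entry and taper rules make a steepening slope plausible for that endpoint. The size depends on the assumed dose mix, share tapering and taper timing. For the other continuous endpoints the loss may be negligible or moderate, depending on how far their baseline slopes diverge. The CMH analysis of the primary endpoint and its stated power are untouched. It is worth correcting because the remedy is almost free, not because the planned analysis would mislead.

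**What to change.** In both MMRM statements of Protocol 7.3, and in SAP 8.3 and 8.5.2, add a baseline-by-visit interaction to the fixed effects. For steroid burden, also add corticosteroid-stratum-by-visit, so that the factor used in randomisation can act at Week 24 with its own effect. Take the Week 24 and Week 48 contrasts from that model.

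Each interaction costs the number of visits minus one: 3 degrees of freedom for the questionnaires at four visits, 6 for steroid burden through Week 24 (seven visits), and 12 through Week 48 (13 visits). Steroid burden needs two such terms. With about 325 subjects this is small, almost nothing is lost if the slopes are in fact equal, and no new data are needed.
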